9.3 POPULATIONS FOR ANALYSES

Using a within-subject comparison, the baseline scan of each MS participant will be compared to that after blockade

9.3.1 Evaluable for toxicity

No toxicity is expected from the radioligand; nevertheless, safety will be monitored as described in Section 8.3. Regarding the two blockers, participants will be asked if they have any discomfort or side effects after its administration and within one to three days after the PET scan via telephone.

9.3.2 Evaluable for objective response

No therapeutic response is expected from the radioligand as we are testing a diagnostic agent at sub-pharmacological doses.

9.3.3 Evaluable Non-Target Disease Response

Not applicable.

9.4 STATISTICAL ANALYSES

9.4.1 General Approach

Two-tailed paired: t-tests will be used to assess whether there are statistically significant differences between PET scans at baseline and after blockade.

ANOVA will be used to assess whether COX-1 and COX-2 binding differs in active, chronic-active, and inactive lesions, and normal appearing white matter.

Correlation analyses will be used to correlate the uptake of COX-1 and COX-2 in the same lesions of the same subjects.

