As a secondary endpoint, we will explore whether different types of MS lesions display different amounts of COX-1 and COX-2 binding. In particular, active lesions will be identified as those that show contrast enhancement with administration of gadolinium. Chronic-active lesions will be identified as those who have a paramagnetic outer rim identified on ME-GRE images that have been processed for quantitative susceptibility maps (QSM). Inactive lesions will be white matter lesions that do not meet criteria for active or chronic-active. Normal appearing white matter will be all white matter minus lesioned white matter, as determined by automated segmentation. We hypothesize that COX-1 and COX-2 binding positively correlates with the activity of the lesion.

Finally, we will determine whether the expressions of COX-1 and COX-2 are correlated by analyzing the uptake of the two tracers within the lesions of the same subjects.

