5 STUDY POPULATION

Patients with MS will be recruited by referral from the PI at UMB, with subjects being those who are currently enrolled under UMB protocol HP-00079860 and who have signed a clause in the UMB consent document allowing contact for future research.

Healthy subjects won't be needed for this study because MS subjects scanned at baseline will be their own controls for the scans after blockade.

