9 STATISTICAL CONSIDERATIONS

9.1 STATISTICAL HYPOTHESIS

- Primary Endpoint: We hypothesize that administration of ketoprofen or celecoxib will reduce COX-1 or COX-2 levels (measured as SUVR between a lesion and a reference region such as the contralateral mirror image of the lesion) in MS lesions. Please note that detectable or specific binding is defined as that which can be displaced by a COX selective inhibitor. Thus, the primary objective “detectable binding” will be assessed with the primary endpoint “displaceable binding.”
- Secondary Endpoint: 1) We hypothesize that more active MS lesions will have higher levels of COX-1 and COX-2 specific binding than less active ones, and that MS lesions will have higher binding than normal white matter. Active lesions will be identified as those that show contrast enhancement with administration of gadolinium. Chronic-active lesions will be identified as those who have a paramagnetic outer rim identified on ME-GRE images that have been processed for quantitative susceptibility maps (QSM). Inactive lesions will be white matter

lesions that do not meet criteria for active or chronic-active. Normal appearing white matter will be all white matter minus lesioned white matter. 2) We hypothesize that the expressions of COX-1 and COX-2 are correlated within the same individuals.

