9.2 SAMPLE SIZE DETERMINATION

Using novel radioligands, this pilot study will attempt to measure the density of COX-1 and COX-2. When the standard deviation and the effect size are unknown, the resource equation method provides an alternative to the power analysis for calculating sample size [24-27]. This method is based on the law of diminishing returns and is normally used in animal experiments to minimize the number of animals committed to an exploratory study. The minimum and maximum sample sizes calculated using the equation are:

$$\text{minimum } n = 10/k + 1$$

$$\text{maximum } n = 20/k + 1$$

where k = number of groups and n = number of samples per group

For example, if there are two groups to compare (e.g., baseline vs blocked studies in the same participants), the minimum $n = 10/2 + 1 = 6$ and the maximum $n = 20/2 + 1 = 11$.

Expressed in other terms, using fewer than six participants per group would have little value because of a high rate of false negatives. On the other hand, using more than 11 participants per group would have diminishing return of true positives.

Following this statistical approach, we request to scan 11 participants per group. Because of the failure rate for completing all scans is 30-40%, we request permission to accrue 16 participants per group.

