9.4.3 Analysis of the Secondary Endpoint(s)

The outcome measure for the secondary endpoint will be SUVR between the lesion and a reference region such as the contralateral mirror image of the lesion, and between the SUVR in the same lesions imaged with both tracers.

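### The secondary ANOVA and tracer correlation in 9.4.1 carry no participant term, although all values come from the same roughly 11 participants

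*Combined protocol and SAP*

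**What the plan says.** Section 9.4.1 gives each secondary objective one sentence. For lesion type: "ANOVA will be used to assess whether COX-1 and COX-2 binding differs in active, chronic-active, and inactive lesions, and normal appearing white matter". For the two tracers: "Correlation analyses will be used to correlate the uptake of COX-1 and COX-2 in the same lesions of the same subjects". Section 9.4.3 adds only the outcome measure, including the comparison "between the SUVR in the same lesions imaged with both tracers".

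The values share participants by design. Section 5 scans no healthy group, because "MS subjects scanned at baseline will be their own controls for the scans after blockade". White matter comes from the same brains as the lesions: "Normal appearing white matter will be all white matter minus lesioned white matter, as determined by automated segmentation" (2.1). On numbers, section 9.2 says "we request to scan 11 participants per group".

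The within-subject statement in 9.3 covers baseline against blockade only. No section says how several lesions from one person enter either secondary test, or what happens to a participant who lacks a class. The eligibility criteria in 5.1 and 5.2 require no particular lesion type.

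**The concern.** Values from one brain are likely to resemble each other. An analysis that ignores this uses the wrong error variance. The ANOVA can then lose power, or reject too often, depending on how lesion types are spread over people. The correlation counts lesions as if they were independent people, and it mixes two associations: whether people with high COX-1 uptake also have high COX-2 uptake, and whether, inside one brain, the lesions high on one tracer are high on the other.

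Missing classes matter too. A standard complete-case repeated-measures ANOVA drops anyone without every class. If, for example, 3 of 11 participants had an active lesion, at most 3 would remain. If these choices are made after lesion counts and values are known, the analyst is choosing between materially different p-values.

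**Working it through.** **Inputs from the plan.** The resource equation with k = 2 gives 10/2 + 1 = 6 and 20/2 + 1 = 11, as stated in 9.2. Accrual of 16 matches 30% non-completion: 11/0.70 = 15.7. At the 30-40% quoted, 16 accrued leave 16 × 0.70 = 11.2 to 16 × 0.60 = 9.6 completers, hence roughly 11.

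**Assumptions.** The documents give no ICC, lesion count, participant-by-class variance or alpha. Used here: 11 participants, total SD 1, two-sided 5%, and ICC and lesion counts over a range. A within-scan ratio to a mirror region may lower the ICC, so 0.1 is included.

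**1. Pooled correlation, no true association at either level.** With m lesions each and equal ICC for both tracers, the variance of r is inflated by about D = 1 + (m − 1) × ICC². The approximate null error is 2 × [1 − Φ(1.96/√D)]. For m = 5 and ICC 0.5, D = 1 + 4 × 0.25 = 2, 1.96/√2 = 1.386, and the error is 16.6%. Simulation (20,000 runs per cell) agrees:

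| ICC | D for m = 3/5/10 | Formula | Simulated |
|---|---|---|---|
| 0.1 | 1.02/1.04/1.09 | 5.2/5.5/6.0% | 5.4/5.4/5.7% |
| 0.3 | 1.18/1.36/1.81 | 7.1/9.3/14.5% | 6.8/8.9/13.6% |
| 0.5 | 1.50/2.00/3.25 | 11.0/16.6/27.7% | 10.5/16.7/27.0% |

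The within-participant correlation and the correlation of participant means stay at about 5% throughout.

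**2. The pooled correlation mixes levels.** With 5 lesions each, within-person r = 0 and between-person r = 0.6, the pooled test is significant in 8/27/54% of runs at ICC 0.1/0.3/0.5. With between-person r = 0.3 it is 6/13/26%. The within-participant test stays at 5%.

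**3. ANOVA, one value per class per person (4 × 11 = 44 values).** Participant effects cancel between class means, so under the null the between-class mean square has expectation 1 − ICC. The one-way error mean square has expectation 1. The F ratio therefore centres near 0.9/0.7/0.5 at ICC 0.1/0.3/0.5. Error df are 44 − 4 = 40 one-way and 3 × 10 = 30 with participant as a block. Power is for a step of 0.35 SD between successive classes.

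| ICC | One-way null error | Power, one-way | Power, blocked |
|---|---|---|---|
| 0.1 | 3.4% | 52% | 56% |
| 0.3 | 1.4% | 49% | 68% |
| 0.5 | 0.4% | 45% | 84% |

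The blocked test has null error of about 5%.

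**4. ANOVA, uneven lesions pooled.** Assume active lesions in 2 people, chronic-active in 5 others, inactive in all 11, and one white-matter value each. With 2/2/5 lesions per affected person (4 + 10 + 55 + 11 = 80 values), one-way null error is 4.9-5.5% at ICC 0.2-0.8. With 3/3/10 (6 + 15 + 110 + 11 = 142 values) it is 7.1/9.9/13.6% at ICC 0.2/0.5/0.8. A participant term gives 4.8-5.3%.

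**5. Why participant-by-class matters.** If 10-20% of the variance is participant-by-class, a participant intercept alone gives 8-45% null error across uneven layouts. A mixed model with both random terms and Kenward-Roger df gives 2.5-6.2%, and participant-by-class means with participant as a block give 3.4-6.0%. The Kenward-Roger range rests on 1,000 runs per cell.

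**The case against.** Several points on the other side stand.

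- **The unit is not wholly missing.** Sections 9.4.1 and 9.4.3 name the lesion as the level at which the tracers are paired. What is missing is how lesions from one person are combined.
- **The plan does not say one-way or pooled.** A reader might infer that it commits to those tests. It does not: the word ANOVA includes repeated-measures forms. But none is stated here, whereas the primary t-test is explicitly paired.
- **The 9.1 hypothesis is ambiguous.** A reader might infer from "We hypothesize that the expressions of COX-1 and COX-2 are correlated within the same individuals" that only a within-participant correlation will do, and that the pooled test fails it. Section 3 and the rationale, "analyzing the uptake of the two tracers within the lesions of the same subjects", fit equally well with both tracers being measured in the same people. On that reading, between-person association supports the hypothesis and the rates in step 2 are not errors.
- **Participant-aware tests can cost power.** With 3 lesions and within-person r = 0.4, the within-participant correlation has about 49% power against 57% pooled at ICC 0.1 if between-person r is 0. If r is 0.4 at both levels, it is about 49% against 65%. The pooled test does not hold its size at higher ICC, so that comparison flatters it.
- **The size is unknown.** At ICC 0.1 the pooled correlation is nearly nominal. The aims are secondary and the study calls itself a pilot.

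The last point limits severity. It does not remove the gap, because the plan still names inferential tests and states hypotheses for them.

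**Conclusion.** The point holds as a gap that should be fixed. The absence of a participant term is certain; its consequences are conditional. If lesions were pooled, the correlation's null error would be about 5-6%, 7-14% and 11-27% at ICC 0.1, 0.3 and 0.5 with 3-10 lesions each. The one-way ANOVA would be conservative in a balanced layout, with power of 45% against 84% at ICC 0.5. It could exceed 5% when a few people supply many active or chronic-active lesions. All of this rests on assumed ICCs, lesion counts and a 5% level.

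Two stronger conclusions are not supported. A reader might infer that ignoring participants always inflates type I error; the balanced ANOVA shows the opposite. A reader might also infer that the primary paired t-test should use one averaged lesion value per person. Section 9.4.2 defines that outcome per lesion, and averaging active with inactive lesions could dilute the signal if active lesions bind more, as 9.1 expects. No change to the primary test is proposed here.

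**What to change.** **Class comparison.** For each tracer, specify a linear mixed model with tissue class fixed, participant random, participant-by-class random where there are several lesions per class, and small-sample degrees of freedom such as Kenward-Roger. Keep participants who lack a class. Name one fallback in advance, participant-by-class means with participant as a block, together with its trigger, such as non-convergence.

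**Tracer correlation.** State that lesions are not treated as independent. Report the within-participant (repeated-measures) correlation and the between-participant correlation of means separately, and state before analysis which one tests the 9.1 hypothesis.

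**Cost.** A few sentences, standard software and no new data. There are fewer degrees of freedom, slightly more analysis work and the possible loss of correlation power described above. The fallback can also be costly in uneven layouts. In one with 3-5 active or chronic-active lesions in each of a few people, at ICC 0.1 and no participant-by-class variance, power for the 0.35 SD step was about 38%. It was 58% with a participant intercept and 64% one-way (null error about 6%). This is why the fallback should have a narrow, stated trigger.

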9.4.7 Sub-Group Analyses

None.

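### The planned COX-1/COX-2 correlation has no lesion-class term, so it cannot show co-expression beyond the shared rise with lesion activity that secondary hypothesis 1 already expects

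*Combined protocol and SAP*

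**What the plan says.** Two secondary hypotheses concern the same lesions.

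- **Hypothesis 1, lesion activity.** Section 9.1: "We hypothesize that more active MS lesions will have higher levels of COX-1 and COX-2 specific binding than less active ones". Section 2.1 expects the same of both enzymes: "We hypothesize that COX-1 and COX-2 binding positively correlates with the activity of the lesion".
- **Hypothesis 2, correlation.** Section 9.1: "We hypothesize that the expressions of COX-1 and COX-2 are correlated within the same individuals". Section 2.1 says this will be examined "by analyzing the uptake of the two tracers within the lesions of the same subjects".

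Section 9.4.1 gives hypothesis 1 an analysis by class: "ANOVA will be used to assess whether COX-1 and COX-2 binding differs in active, chronic-active, and inactive lesions", with normal appearing white matter as a further level. Hypothesis 2 gets "Correlation analyses will be used to correlate the uptake of COX-1 and COX-2 in the same lesions of the same subjects", and section 9.4.3 gives its outcome as a comparison "between the SUVR in the same lesions imaged with both tracers". Neither section attaches a lesion-class term, stratum, partial correlation or participant term to the correlation. Section 9.4.7 lists no sub-group analyses.

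**The concern.** Hypothesis 1 says that active lesions have more of both enzymes. If so, active lesions sit high on both axes of the COX-1/COX-2 scatter plot and inactive lesions sit low on both. That alone tilts the cloud upward. A positive r could then arise in two ways: the enzymes go together among lesions of the same class, or each follows lesion activity separately with no further link. The planned analysis does not tell these apart.

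The protocol lists the correlation as its own secondary objective (section 3) beside the lesion-type comparison. What is at stake is how much a positive result would add to the ANOVA, and whether it could be taken as co-expression at equal lesion activity when it does not show that.

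**Working it through.** **The plan's own figures.** The protocol gives no expected correlation, effect size, SD, class mix or lesion count; section 9.2 says that the SD and effect size are unknown. The one usable input is the number scanned: 20/2 + 1 = 11 participants, which reproduces.

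**Step 1: sign.** By the law of total covariance, the covariance across all lesions equals the average within-class covariance plus the covariance of the class means. Set the first term to zero. If both sets of class means rise with activity and at least two classes are present, the second term is strictly positive, and so is the expected pooled r.

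**Step 2: size.** Assumptions: class scores 0, 1, 2 for inactive, chronic-active, active; each tracer's mean rises D/2 within-class SDs per step; no within-class correlation; class mix 75/15/10%. The variance of the class score is

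V = (0.15 × 1 + 0.10 × 4) − (0.15 + 0.20)² = 0.55 − 0.1225 = 0.4275.

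Then r = V(D/2)² / [1 + V(D/2)²]. At D = 2 this is 0.4275/1.4275 = 0.30. At D = 1 it is 0.1069/1.1069 = 0.10.

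**Step 3: how often it is significant.** Simulation, 4,000 data sets per cell, independent lesions, two-sided 5% Pearson test (level and sidedness assumed; the plan states neither for the correlation):

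| D | Expected pooled r | Significant, 50 lesions | Significant, 100 lesions |
|---|---|---|---|
| 0.5 | 0.03 | about 5% | about 6% |
| 1 | 0.10 | about 10% | about 16% |
| 1.5 | 0.19 | about 27% | about 50% |
| 2 | 0.30 | about 56% | about 85% |

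With class means removed from both tracers, the test rejects in about 5% of trials in every cell.

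**Step 4: sensitivity to the mix.** With equal classes (V = 2/3), r is 0.14 at D = 1 and 0.40 at D = 2. With 2% active, 10% chronic-active and 88% inactive (V = 0.1604), it is 0.04 and 0.14. If only one tracer follows activity, or only one class is present, it is 0.

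**Step 5: is class adjustment enough?** Spread the lesions over 11 participants and give each tracer its own independent participant effect, with an assumed intraclass correlation of 0.3 to 0.5. The class-only adjusted test then rejects a true null in about 8–16% of trials with 50 lesions and 12–25% with 100. With participant added as a factor, it returns to about 5%.

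**The case against.** The strongest reply is that the plan answers the question it asks. Hypothesis 2 is never conditioned on lesion class. If activity raises both enzymes, lesions high in one are high in the other, and a positive r is a true answer. The rejection rates in the table are therefore not false positives for hypothesis 2 as written. That stands. A reader might infer that a pooled positive r is spurious or merely repeats hypothesis 1. The documents do not support this: no section asks for association at equal activity, and the pooled r also carries any within-class association.

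Second, activity is the biology under study, not clearly a nuisance. Adjusting for class changes the question, and an adjusted r near zero would not mean that the enzymes fail to rise together. This stands too, and is why the adjusted estimate should sit beside the pooled one and not replace it.

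Third, the protocol never says that classes are pooled; its wording is simply unspecific. Pooling is the plain reading, since class appears only in the ANOVA sentence and no sub-group analysis is planned, but it remains a reading.

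Fourth, it is tempting to say that r turns positive whenever hypothesis 1 is true. That holds only for the expected value. At D = 0.5 the pooled test rejects at close to the nominal rate.

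Finally, the ANOVA will show class differences beside the correlation, in a study that calls itself a pilot. This lowers the stakes but does not supply the missing estimate.

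**Conclusion.** The point holds in limited form. As section 9.4.1 reads, the correlation cannot separate co-expression at equal lesion activity from two enzymes that each follow activity, and no other planned analysis does so. The sign of the effect follows from hypothesis 1 holding for both tracers with at least two classes present. Its size does not follow from the documents. Under the assumed 75/15/10% mix it ranges from negligible (r about 0.03 at D = 0.5) to material (about 0.30 at D = 2), and it is smaller if active lesions are rarer.

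The plan is not wrong about hypothesis 2 as worded. What needs limiting is what the pooled r may be said to show. This is a cheap improvement to a secondary analysis and does not touch the primary endpoint.

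**What to change.** In section 9.4.1, add two sentences to the correlation paragraph:

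1. Beside the correlation across all lesions, report a correlation adjusted for lesion class and participant, with both entered as factors for both tracers. The participant term also suits the within-individual wording of hypothesis 2.
2. State that the pooled r describes the overall association, and that any claim of co-expression beyond shared lesion activity rests on the adjusted estimate.

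**Cost.** Wording only. Lesion class is already assigned from MRI by investigators blinded to PET (sections 2.1 and 9.1), so no scan, visit or participant is added. Adjustment uses 2 degrees of freedom for class and 10 for 11 participants, 12 in all. With 50 lesions the standard error on Fisher's z scale goes from 1/√47 = 0.146 to 1/√35 = 0.169, an interval about 16% wider. The adjusted r also leaves out co-expression driven by lesion activity itself, so neither estimate should be reported alone.

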9.4.2 Analysis of the Primary Endpoints

The outcome measure for the primary endpoint will be SUVR between the lesion and a reference region such as the contralateral mirror image of the lesion.

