2 INTRODUCTION

2.1 STUDY RATIONALE

Our laboratory developed two novel radioligands, [¹¹C]PS13 and [¹¹C]MC1 for PET imaging of cyclooxygenase-1 (COX-1) and cyclooxygenase-2 (COX-2), respectively. COX-1 and COX-2 are two isoforms of COX enzyme which play a key rate limiting step in the conversion of arachidonic acid (AA) into pro-inflammatory lipid metabolites called prostaglandins (PGs). COX-1 is constitutively expressed in most brain tissues whereas COX-2 is induced by inflammatory stimuli. We recently found that COX-2 was elevated and measurable in the currently symptomatic joints of patients with rheumatoid arthritis [1]. We now seek to determine whether COX-2 is measurable in the brains of participants with MS, in particular in the MS plaques.

Although MS provides the technical advantage of local areas of active inflammation, it also entails the technical disadvantage of a breakdown of the blood-brain barrier surrounding active plaques. Thus, the uptake could reflect both parent radioligand binding to COX-1 and COX-2 as well as inactive, polar radiometabolites that can spill into the compromised tissue. To address this problem, a COX-1 and COX-2 blocking agent, ketoprofen and celecoxib, will be given. Radioligand specific uptake will be blocked by ketoprofen and celecoxib, whereas the activity due to radiometabolites won't be affected.

In this way, the outcome measure will be a comparison of brain lesions at baseline and after blockade, normalized to a reference region such as the contralateral mirror image of the lesion, and thus does not require absolute quantitation with arterial plasma samples. Of course, this ratio would not determine whether COX-1 or COX-2 are globally increased in MS brain, in addition to any local increases associated with active plaques. However, arterial blood sampling seems excessively burdensome for an exploratory study. Expressed in other terms, if COX-1 or COX-2 do not detect any specific binding in MS lesions, then it's unlikely to detect a global increase compared to healthy subjects.

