A reference region will be selected based on the PET scan blocked by celecoxib or ketoprofen. A true reference region has no specific/blockable binding, and a pseudo-reference region has a small amount of specific binding. The cerebellum might not be the most appropriate choice because the cerebellum is affected by diffuse inflammation in MS. This is however a problem common to all regions, since MS affects the whole brain. A more accurate reference region might be the mirror image of the ROI in the opposite hemisphere because, even if affected by generalized inflammation, the contralateral ROI would more accurately reflect the amount of nonspecific binding of the target region. A comparison with the contralateral region would track the change in COX-1 and COX-2 binding after blockade with sufficient accuracy, without the need of an arterial input function.

The MS lesions will be identified anatomically by a 7T MRI, acquired under a specific protocol of UMB (PI: [name]). The 7T MRI images include the following brain sequences: MP2RAGE (magnetization prepared 2 rapid acquisition gradient echo), MPRAGE (magnetization prepared rapid acquisition gradient echo), FLAIR (fluid attenuated inversion recovery), and a ME-GRE (multi-echo gradient recalled echo). All are 3D acquisitions and acquired both pre- and post-gadolinium contrast. All 7T MRI images will be co-registered to the pre-contrast MP2RAGE T1-weighted image at 0.5 mm³ resolution. MRI images will undergo both manual processing for MS lesion identification and classification, along with use of

automated and semi-automated tools for brain structure/tissue segmentation. PET images will also be co-registered to the pre-contrast T1-weighted MP2RAGE image, allowing interrogation of PET signal in various lesion types and brain structures. Every effort will be made to have PET study visits occur as close to the date of the 7T MRI as possible. In order to account for logistical problems, PET will be performed within 180 days before or after MRI. Similarly, the baseline/blocked scans will be performed within two months of each other. An interval of at least two days will be respected between the administration of the two blockers (ketoprofen and celecoxib). Lesions will be identified on MRI independently of the PET scans and by investigators blinded to the PET scans.

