3 OBJECTIVES AND ENDPOINTS

Objectives	Endpoints	Justification for Endpoints
Primary		
To determine whether COX-1 and COX-2 are detectable in the brains of participants with MS.	PET scans with [¹¹ C]PS13 and [¹¹ C]MC1 with and without blockade by ketoprofen and celecoxib.	We previously demonstrated that these radioligands are selective for COX-1 and COX-2.
Secondary		
To determine whether COX-1 and COX-2 differ in various types of MS lesions (active, chronic active, inactive) compared to normal white matter.	PET scans with [¹¹ C]PS13 and [¹¹ C]MC1 with and without blockade by ketoprofen and celecoxib.	We previously demonstrated that these radioligands are selective for COX-1 and COX-2.
To determine whether the expressions of COX-1 and COX-2 are correlated in the lesions of the same subjects	PET scans with [¹¹ C]PS13 and [¹¹ C]MC1 with and without blockade by ketoprofen and celecoxib.	We previously demonstrated that these radioligands are selective for COX-1 and COX-2.

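### With a blockable reference region, the primary SUVR change tests lesion against reference, so a null result does not show that displaceable binding is absent

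*Combined protocol and SAP*

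**What the plan says.** Section 3 gives the primary objective: "To determine whether COX-1 and COX-2 are detectable in the brains of participants with MS". Section 9.1 makes it operational: "detectable or specific binding is defined as that which can be displaced by a COX selective inhibitor". That definition concerns the lesion alone and does not mention excess over another region.

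The planned evidence is a ratio. Section 9.4.2 sets the outcome as "SUVR between the lesion and a reference region such as the contralateral mirror image of the lesion", and section 9.4.1 plans two-tailed paired t-tests of "differences between PET scans at baseline and after blockade". The mirror region is given as an example, but it is the only reference named in 9.1 and 9.4.2.

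Section 2.1 covers the choice of reference. It says the region will be selected from the blocked scan and gives a criterion: "A true reference region has no specific/blockable binding". It then leans towards the mirror because the mirror should match the lesion's nonspecific binding, and says this comparison follows the change in binding accurately enough without arterial sampling. It sets no threshold for calling a region unblockable and no fallback.

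Section 2.1 also concedes that "this ratio would not determine whether COX-1 or COX-2 are globally increased in MS brain". It closes by arguing that if no specific binding is found in lesions, the tracers are "unlikely to detect a global increase compared to healthy subjects".

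**The concern.** The objective asks whether lesion signal can be displaced. A lesion/reference ratio answers that only if the reference is not displaced as well. If it is, the test asks whether the lesion's displaceable fraction (displaceable signal as a share of total signal) is larger than the reference's.

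The protocol's own background suggests the mirror is displaced. Section 2.2 reports COX-1 in all brain areas, and displaceable COX-2 signal in every one of six healthy subjects.

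Section 2.1 adds a second route to a misleading result. It warns of "inactive, polar radiometabolites that can spill into the compromised tissue" around active plaques and relies on blockade to separate this from binding. In a ratio to the mirror, that extra nondisplaceable signal dilutes the lesion's displaceable fraction. It can cancel or reverse the SUVR change.

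Section 9 plans no separate test of lesion displacement, and section 5 excludes healthy controls. A null ratio could therefore be reported as not detectable when that does not follow. Because the reference is chosen from the blocked scans with no written rule, the primary outcome is also not fully defined until those scans have been seen.

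**Working it through.** **Figures from the plan.** Mean V_T/fp in healthy brain is 95 at baseline and 76 after celecoxib (section 2.2): (95 − 76)/95 = 20.0%, the top of the stated 10-20% range. The target is 20/2 + 1 = 11 completers (section 9.2). With 16 accrued and 40% failure, 16 × 0.6 = 9.6 remain, so n = 9 is also shown.

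**General result.** Let dL and dR be the displaced fractions of lesion and reference. Then

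SUVR blocked / SUVR baseline = (1 − dL)/(1 − dR).

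This equals 1 whenever dL = dR, whatever the baseline SUVR. For dL = 20%:

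- dR = 0: SUVR changes by −20.0%
- dR = 10%: −11.1%
- dR = 20%: 0.0%

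If dL = 10% and dR = 20%, SUVR rises by 12.5%.

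**COX-2 illustration.** Set the mirror signal to 1, of which f is displaceable (f = 0.10 or 0.20). Let r be the lesion/mirror ratio of nondisplaceable signal and m the lesion/mirror ratio of displaceable binding. With full block:

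- SUVR baseline = r(1 − f) + mf
- SUVR blocked = r
- SUVR change = r/[r(1 − f) + mf] − 1, which is 0 when m = r
- lesion displaced = mf/[r(1 − f) + mf]

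| r | m | Lesion displaced | SUVR change |
|---|---|---|---|
| 1.0 | 1 | 10-20% | 0% |
| 1.0 | 2 | 18-33% | −9 to −17% |
| 1.0 | 10-20 | 53-83% | −47 to −79% |
| 1.3 | 1 | 8-16% | +2 to +5% |
| 1.3 | 1.3 | 10-20% | 0% |
| 1.3 | 10-20 | 46-79% | −40 to −74% |

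In the fourth row, SUVR goes from 1.27 (f = 0.10) or 1.24 (f = 0.20) to 1.30. The value r = 1.3 is an assumption standing for radiometabolite spill.

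**Smallest lesion binding the test can find.** For a two-sided paired t-test at an assumed alpha of 0.05 (noncentral t), 80% power needs a standardised change d of 0.938 at n = 11 and 1.067 at n = 9. The smallest m is [r/(1 − d·SD) − r(1 − f)]/f. In each range the first value is for f = 0.20 and the second for f = 0.10.

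| Assumed SD of SUVR change | n = 11, r = 1 | n = 9, r = 1 | n = 11, r = 1.3 |
|---|---|---|---|
| 5% | 1.2-1.5 | 1.3-1.6 | 1.6-1.9 |
| 10% | 1.5-2.0 | 1.6-2.2 | 2.0-2.6 |
| 15% | 1.8-2.6 | 2.0-2.9 | 2.4-3.4 |

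When m = r the rejection rate is 5% at every n and SD.

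**What lesion SUV alone could add.** Power at n = 11 with d = f/SD:

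| Displacement | SD of SUV change 15% | SD 25% |
|---|---|---|
| 10% | 0.515 | 0.225 |
| 20% | 0.978 | 0.668 |

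If tracer delivery rose by an assumed 10% after blockade, the SUV changes would be 0.90 × 1.10 − 1 = −1% and 0.80 × 1.10 − 1 = −12%.

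**The case against.** The strongest reply is that the problem is conditional. The mirror is only an example, section 2.1 defines a true reference, and a region with no blockable binding would remove the difficulty. That is correct, but section 2.1 gives no threshold or fallback and then prefers the mirror on other grounds.

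Second, the evidence that the mirror is blockable is indirect. The 10-20% comes from V_T/fp in healthy brain, not from SUV in white matter opposite an MS lesion. For COX-1 the documents give presence in brain but no human brain displaceable fraction; the human ketoprofen figures concern peripheral organs. This limits the illustration, and COX-1 cannot be quantified. The algebra is not affected.

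Third, the protocol expects upregulation, says it can reach 10- to 20-fold, and elsewhere asks about local elevation, which a lesion/mirror ratio suits. This stands: large upregulation would be seen. But no upregulation figure for MS is given, and the primary objective is detectability.

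Fourth, nothing in section 9 says a null will be read as absence, and section 2.1 admits the ratio cannot show a global increase. That admission does not cover lesion binding that is present but matched by the reference. The closing argument of section 2.1 needs exactly that step.

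Finally, SUV without arterial input may be biased as well as noisy. This is accepted, and it is why SUV change can only be supportive.

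**Conclusion.** The concern holds and should be fixed. With a blockable reference, the planned test can return a null, or even a rise, while the property that section 9.1 defines as detectable is present. A significant fall in SUVR would still support detectable lesion binding; the weakness is in reading a null.

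The exposure is to no or modest local elevation. At 11 completers and an assumed 10% SD, lesion COX-2 binding must be about 1.5-2.0 times the mirror's for 80% power, or 2.0-2.6 times with 30% extra nondisplaceable lesion signal.

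These sizes assume full blockade, transfer of the healthy-brain 10-20% to SUV in the mirror, alpha 0.05 and the SDs shown. The documents give no SD, alpha, white-matter fraction or radiometabolite contribution. The general result, that equal fractions give no change, needs none of these assumptions.

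**What to change.** 1. **State what a null means.** In 9.1 and 9.4.2 add wording such as: *The baseline-to-blocked SUVR change tests whether the displaceable fraction of the lesion signal exceeds that of the reference region. A null result means no such excess was shown; it does not show that displaceable binding is absent.* Qualify the closing inference and the accuracy statement in section 2.1 to match.
2. **Report the two parts of the ratio.** From the same scans, give the baseline-to-blocked change in lesion SUV and in reference SUV separately, with confidence intervals, as supportive evidence on detectability.
3. **Write the reference rule.** Use one group-wide rule per tracer, with candidate regions, a criterion for not blockable, and a fallback, set before lesion outcomes are analysed. The criterion should compare baseline with blocked scans, since a blocked scan alone cannot show what was displaced. The six healthy baseline/blocked studies in section 2.2 can inform the rule for [11C]MC1. If the fallback is the mirror, report the limitation in item 1 with the result.

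The cost is wording in 2.1, 9.1 and 9.4.2, a short rule, and two extra outputs per lesion. The primary test and the scans are unchanged. The downside is that SUV is noisy and sensitive to tracer delivery, as the power and delivery figures above show, so it should stand beside the ratio and not replace it.
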